1. STUDY OBJECTIVES/HYPOTHESIS

Our research group has successfully developed a system of assessment methodologies and statistical techniques that can accurately assess energy balance and estimate energy intake [EI] using research-grade but non-gold standard techniques.¹⁶⁻¹⁸ The purpose of this study is to apply these techniques using consumer devices to assess rate of energy storage [ES] and energy expenditure [EE], then estimate EI using the intake-balance technique.

We believe calibration models developed in the proposed study will be able to be translated to other consumer devices with only minor modifications given common hardware (e.g. triaxial accelerometry), resulting in overall improved ability to assess energy balance and EI at a population level and positive health outcomes.

Aim 1. Validate and calibrate consumer devices to estimate energy balance using gold-standard methods and a Bayesian semi-parametric approach. *Hypothesis 1:* We will be able to jointly model measurement error for both EE and ES to create a calibration model that reduces bias and improves accuracy of consumer devices of EE and ES.

Aim 2. Estimate energy intake using the intake-balance technique using consumer monitors. *Hypothesis 2:* We will use calibrated EE and ES from consumer monitors to estimate EI using the intake-balance technique, with values being superior to self-reported EI.

2. RATIONALE

The challenges of accurate estimation of energy intake are well-documented.⁵⁻⁷ Recently, mathematical models have been formulated based on the principles of the first law of thermodynamics (rate of energy storage [ES] = rate of energy intake [EI] – rate of energy expenditure [EE]).⁸ that allow researchers to estimate energy balance. For example, if one is able to accurately measure two of the variables of the energy balance equation (e.g., changed ES and rate of EE), it is mathematically possible to solve for the third (e.g., EI). Based on a variety of existing data sets containing EE, EI, and changes in ES (e.g., body composition using a two-compartment model of fat mass and fat-free mass), researchers have developed and refined a technique termed the intake-balance method to estimate EI.⁹⁻¹¹ The result is a simple, easy-to-use equation that offers great promise in the quest for estimating EI using objectively measured methods.

A current limitation in using the intake-balance method to estimate EI is the feasibility in measuring EE and ES. While both can be accomplished with a high degree of accuracy, the gold-standard methods of assessment of each (doubly-labeled water [DLW] for EE, dual-energy absorptiometry [DXA] for ES) is too costly and resource-intensive for most applications. Alternatively, consumer devices designed to measure physical activity and body composition are generally affordable, easy to use, and popular (an estimated 45 million will be sold in 2017),¹² but have varying levels of validity and reliability.¹³⁻¹⁵

3. STUDY DESIGN

There are four stages in the proposed project:

1. We will validate EE and ES (hereafter, Fitbit_EE and Fitbit_ES) from a consumer physical activity monitor (Fitbit Alta HR™) and body composition analyzer (Fitbit Aria™) with gold-standard measures of DLW for EE and DXA for ES during an initial 14- day baseline period;
2. We will estimate EI using the intake-balance method during the 14-day baseline period;
3. We will calibrate daily Fitbit_EE and Fitbit_ES from consumer devices using a Bayesian semi-parametric measurement error modeling approach to estimate energy balance during a second 14-day period immediately following the baseline period.
4. We will reassess our validation and calibration models of consumer devices during a third 14-day assessment period to evaluate changes associated with growth and development with gold-standard measures of DLW for EE and DXA for ES.

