4. TARGET STUDY POPLUATION SPECIFICS

Participants will include 24 children or adults, ages 8-90. Participants will be recruited from the community. We intend to enroll participants within the same family (child, parents, and siblings) as long as they meet the age criteria.

Inclusion Criteria

- Healthy children and adults, aged 8-90.
- Able to be physically active.

Exclusion Criteria

- History of restrained eating, eating disorders, bariatric surgery, or other significant medical diagnosis that could impact metabolism.
- Participants taking thyroid medications, beta blockers, or other stimulants (medications are known to affect metabolism).

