5. DATA COLLECTION

Data Collection Procedures

The study will include 4 visits to CMH and assessments to be conducted at home.

Participants will receive a Fitbit Alta HR™, a wristworn tri-axial activity monitor with optical heart rate monitoring (**Figure 1**, top), and a Fitbit Aria™ smart scale which measures fat mass and fat-free mass using bioimpedance (**Figure 1**, bottom). Participants will be instructed to wear the monitor at all times (except for swimming or showering) and measure their body composition on the scale daily for 6 weeks. Fitbit_EE and Fitbit_ES will be uploaded using Bluetooth and Wi-Fi, respectively, to the Fitbit Dashboard™ and accessed by study staff using Fitabase™, a research platform that collects data in collaboration with Fitbit, Inc. Fitbit_EE and Fitbit_ES will be calibrated during two 14-day assessment periods (study start and study end) using DLW and DXA. ‘True’ EE will be measured using a standard 14-day DLW protocol¹⁹ with samples collected on Day 0, 7, and 14. ‘True’ ES will be calculated using DXA measurements on Day 0 and Day 14. Fitbit_EE and Fitbit_ES during the assessment period will then be calibrated to ‘true’ EE and ES using a Bayesian semi-parametric approach, using free knot splines and Reversible Jump MCMC algorithms previously developed through work in our lab.¹⁸ This calibration model will then be applied to daily Fitbit_EE and Fitbit_ES collected during the middle 14-day assessment period to assess daily energy balance. Finally, we will estimate EI from Fitbit measurements using the equation^{16, 17}:

$$\text{calculated energy intake} = 1,020 \frac{\Delta FFM}{\Delta t} + 9,500 \frac{\Delta FM}{\Delta t} + EE$$

Where ΔFFM and ΔFM represent change in each variable; Δt represents days between start and end of an assessment period; 1,020 represents the energy density in kcals of FFM per kg; and 9,500 represents the energy density of FM per kg, both based on established values;²⁰ EE represents daily energy expenditure during the assessment period.

Doubly-labeled Water Procedures

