6. STUDY DURATION/STUDY TIMELINE

Target start date is July 2017

Stage 2, recruitment and data collection, January 2018 – June 2018

Stage 3, data analysis and manuscript development, June 2018- August 2018

Total study duration will be 1 year.

We will recruit potential participants from the community, which could include CMH patients, employees, or students. We plan to post a recruitment flyer within CMH in clinic areas and employee breakrooms, as patients, employees, or students would be eligible to participate. Potential participants from the community will then contact us from the information on the flyer if they are interested in the study.

Once potential participants are identified and express interest, we will schedule an orientation (visit 1) at CMH Don Chisholm during which informed consent will be obtained. Participants will be given the Actigraph activity monitor, the FitBit tracker, the FitBit scale, and be trained on how to use them. Participants will complete the DXA and the DLW procedures. The day zero urine sample will be obtained at visit 1.

After visit 1, participants will be asked to complete the urine samples at home (day 8). Participants will also be contacted to complete the diet recall procedures. Participants will be asked to wear the FitBit tracker and use the FitBit Scale daily starting at visit 1 until the end of the study. The Actigraph monitor will be worn between visit 1 and 2, and visit 3 and 4.

Visit 2 will occur 2 weeks after visit 1. Urine samples will be returned. A DXA will be obtained.

Visit 3 will occur 4 weeks after visit 1. Procedures at visit 3 are identical to visit 1.

Visit 4 will occur 2 weeks after visit 3. Procedures at visit 4 are identical to visit 2.

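### Stage 4 is meant to evaluate growth and development, but two criterion periods 28 days apart in people aged 8 to 90 can show only short-term reproducibility of the calibration

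*Protocol*

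**What the plan says.** Protocol Section 3 lists four stages. Stage 1 validates the devices against "gold-standard measures of DLW for EE and DXA for ES during an initial 14- day baseline period". Stage 3 covers daily energy balance "during a second 14-day period immediately following the baseline period". Stage 4 reassesses the validation and calibration models in a third 14-day period, and gives the reason as "to evaluate changes associated with growth and development".

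Section 6 fixes the calendar: "Visit 3 will occur 4 weeks after visit 1", and "Visit 4 will occur 2 weeks after visit 3". Section 5 agrees, since participants are to "measure their body composition on the scale daily for 6 weeks". Section 5 also says that the devices are calibrated to DLW and DXA in both the first and the last period, and that the resulting model is applied to the middle one.

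Section 4 sets the population: "Participants will include 24 children or adults, ages 8-90". It gives no quota, age stratum or minimum number of children. Neither numbered aim in Section 1 mentions growth or development. Section 7 describes a pilot whose size rests on available resources.

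**The concern.** Interval, population and purpose are all fixed in the protocol, and the first two do not serve the third. An analysis plan could not repair this, because it cannot lengthen the interval or supply children who were not enrolled. A sample made up wholly of adults would comply with Section 4, and in such a sample the stated purpose of stage 4 would have no subject matter.

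What is at stake is what stage 4 may conclude. If the calibration differs between the first and third periods, the stated purpose invites a developmental reading that the data cannot support. If it does not differ, the same purpose invites the reading that the calibration holds up under growth, when little or no growth took place. The pilot is meant to inform a larger study, so either reading could be carried into that study's planning.

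**Working it through.** **1. Timeline (figures from Sections 3, 5 and 6).**
- Three periods of 14 days: 3 × 14 = 42 days = 6 weeks, which reproduces the stated follow-up.
- Visits fall on days 0, 14, 28 and 42. Criterion periods: days 0–14 and 28–42.
- Midpoints are day 7 and day 35, so the separation is 35 − 7 = 28 days. As a share of a year, 28 / 365.25 = 7.7%.

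**2. How much a child might grow in 28 days.** The protocol gives no growth rate. Assume 2–6 kg and 5–8 cm a year.
- Weight: 2 × 28/365.25 = 0.15 kg; 6 × 28/365.25 = 0.46 kg.
- Height: 5 × 28/365.25 = 0.38 cm; 8 × 28/365.25 = 0.61 cm.

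Growth in children is therefore small but not zero. In adults it is nil.

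**3. What that means for energy storage (ES).** Use the Section 5 energy densities (9,500 kcal per kg fat mass, 1,020 kcal per kg fat-free mass) and assume that 20% of the gain is fat.
- At 2 kg a year: (0.2 × 2 × 9,500 + 0.8 × 2 × 1,020) / 365.25 = 5,432 / 365.25 = 15 kcal/day.
- At 6 kg a year: 16,296 / 365.25 = 45 kcal/day.

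Steady growth adds this at nearly the same rate in both periods, so its contribution to the between-period difference in ES is close to zero.

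**4. Criterion noise on the same scale.** By the protocol's equation, a 0.1 kg error in fat-mass change over 14 days is 9,500 × 0.1 / 14 = 68 kcal/day. The period-3 minus period-1 difference in ES uses four scans. With an assumed independent fat-mass error of SD s per scan, its SD from that source alone is 9,500 × 2s / 14:
- s = 0.1 kg: 136 kcal/day.
- s = 0.5 kg: 679 kcal/day.

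This noise also enters any change in the device-minus-DXA difference.

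**5. Size of change that the sample could resolve.** The protocol states no power target, so this is only a yardstick. Take 80% power, two-sided 5% and a normal approximation. The smallest mean within-person change is (1.960 + 0.842) / √n, in units of the SD of that change:
- n = 24: 0.57.
- n = 12: 0.81.
- n = 6: 1.14.

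With the SDs in step 4 and n = 24, this is about 78 to 388 kcal/day for ES.

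**6. Attribution.** Growth and elapsed time move together in every participant. The only built-in comparison would be children against non-growing adults, and the protocol does not fix how many of each there will be. With an even split of 12 and 12, assumed for illustration, the detectable difference in mean change is 2.802 × √(1/12 + 1/12) = 1.14 SD. Even then, children and adults could differ in how their wear or behaviour changes over six weeks. No feature of the design separates growth from these or from measurement error.

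**The case against.** The best defence is that this is a pilot, that neither numbered aim depends on growth, and that the phrase is one clause in a stage description. That stands, and it limits the weight of the point. It does not rescue the clause, because pilot status excuses imprecision but not a purpose that the interval cannot serve.

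Several stronger readings are tempting, and the documents do not support them.
- A reader might infer that growth in four weeks is too small to record. Section 5 records weight to 0.1 kg and height to 0.1 cm, from the average of three measurements. On the rates assumed above, the gain is about 1.5 to 4.6 weight units and 4 to 6 height units. A visible height gain is still not evidence of a change in device calibration.
- A reader might reach for a power calculation on mean energy expenditure. Stage 4 concerns the relation of device to criterion, and mean expenditure can shift while that relation stays the same, or the reverse.
- A reader might add season or the second DLW dose as confounders. The protocol gives no mechanism for either, and visit 3 repeats the visit 1 procedures, including the day-zero urine sample.
- A reader might assume that device wear will fall. The protocol does not say so, and Section 5 says that wear information may be available in real time. That would help to describe wear, but it does not isolate growth.
- A reader might say that the results will be reported as development. No hypothesis, endpoint or reporting rule in the protocol says this.

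**Conclusion.** The point holds as a mismatch between a stated purpose and the design. The interval of 28 days and the open age range come directly from the protocol, and the conclusion on attribution needs no assumed figure. The growth amounts, the fat share and the DXA error are assumptions. They show scale only: growth of tenths of a kilogram or centimetre, with a near-zero contribution to the change in ES, against criterion noise of about 136 to 679 kcal/day per person.

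It does not follow that the third period is wasted or that a study aim fails. The period is a sound repeat assessment, and growth is a purpose of one stage rather than an aim. Severity is minor to moderate.

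**What to change.** In Section 3, stage 4, replace the growth-and-development purpose with short-term reproducibility of the calibration over the six weeks, and state that developmental change is left to the larger study.

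Add one analysis, in this order:
1. Apply the calibration fitted in period 1, unchanged, to the period-3 device data. Report its bias and error against DLW and DXA, descriptively for children and adults where numbers allow.
2. Then fit the two-period calibration that Section 5 already plans, for use in the middle period.

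The order matters. Once period 3 has helped to fit the model it cannot test it independently, while holding it out for good would remove half the criterion periods from a flexible model fitted to 24 people. The first step is therefore an added check and not a replacement.

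The cost is a little more analysis and the loss of one purpose clause. No new visits, procedures or data are needed. The child and adult summaries may be thin, since the mix is not fixed, and should carry no formal comparison.

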4. TARGET STUDY POPLUATION SPECIFICS

Participants will include 24 children or adults, ages 8-90. Participants will be recruited from the community. We intend to enroll participants within the same family (child, parents, and siblings) as long as they meet the age criteria.

Inclusion Criteria

- Healthy children and adults, aged 8-90.
- Able to be physically active.

Exclusion Criteria

- History of restrained eating, eating disorders, bariatric surgery, or other significant medical diagnosis that could impact metabolism.
- Participants taking thyroid medications, beta blockers, or other stimulants (medications are known to affect metabolism).

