7. STATISTICAL CONSIDERATIONS

Measures

- Primary measures: Energy intake, energy expenditure and body composition
- Secondary measure(s): Demographics

General Design Issues

The proposed pilot study is a calibration study, which will generate data needed for a larger study.

Sample size determination

As a pilot study, we will have resources to collect data from N=24 participants. We will use this data to determine power requirements for a larger study.

Data Analyses

Statistical significance for comparison between the different data collection methodologies will be tested using analysis of variance (ANOVA) for continuous variables and chi-square tests for categorical variables. Statistical significance will be set at P<.05 (two-sided) for all analyses.

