8. HUMAN SUBJECTS

Institutional Review Board (IRB) Review and Informed Consent

The IRB of record is Children's Mercy Hospital.

This protocol, and any subsequent modifications, will be reviewed and approved by the Pediatric IRB at The Children's Mercy Hospital & Clinics.

Potential participants will be recruited from the community.. Once the participants are contacted by CMH study staff, they will be given more details about the study and sent the consent form to review.

The study team will do a 10 minute phone screening with the parent to determine eligibility, and will schedule a time for the parent and child to come in for an orientation. The parent and child will then come to the Don Chisholm center at CMH for visit 1. The consent form will be reviewed and ample time will be given for the parent and child to consider participation. Prior to performing any procedures related to this study, the permission/assent form or consent form will be reviewed carefully with the participant and parent in person.

Subject Confidentiality

All records will be kept in a locked file cabinet. Human subject's names will be kept on a password protected database and will be linked only with a study identification number for this research. There are no patient identifiers recorded in the research record. All computer entry and networking programs will be done using study identification only. All data will be entered into a computer that is password protected. Data will be stored in a locked office of the investigators and maintained for a minimum of three years after the completion of the study.

Subject Payment

Subjects will be paid via ClinCard \$50 total for participation. Payment will be given in \$25 increments at visit 2 and visit 4 once the Actigraph activity monitor is returned. SSN is required for payment, and will be entered directly into the Greenphire secure website. SSN will not be retained in the subject's study file. Participants may also be compensated for mileage or a hotel stay based on their distance traveled (they will be given a choice of one or the other).

Participants will be able to keep the Fitbit Alta HR™ activity tracker (\$150 value) and the Fitbit Aria™ smart scale (\$130 value). If participants are within the same family, they will be given one Fitbit Aria™ smart scale per household.

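### Family members are enrolled and share one scale, but the named significance tests have no household or within-person term, so their P values may be too small or too large

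*Protocol*

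**What the plan says.** - **Sampling.** Protocol section 4 sets the sample: "Participants will include 24 children or adults, ages 8-90". It then says: "We intend to enroll participants within the same family", naming children, parents and siblings within the age limits. Clustering by family is therefore intended. The number and size of families are not given.
- **Equipment.** Under Subject Payment in section 8, where participants belong to one family, "they will be given one Fitbit Aria™ smart scale per household". The wrist monitor is not described as shared.
- **Tests.** Under Data Analyses in section 7, comparisons between data collection methods "will be tested using analysis of variance (ANOVA) for continuous variables", with chi-square tests for categorical variables, at two-sided P<.05 throughout. No term for household or person is named.
- **Calibration.** Section 5 describes a Bayesian semi-parametric model with free knot splines. It does not say how dependence between people is handled.
- **Purpose.** Section 7 bases the sample size on resources ("As a pilot study, we will have resources to collect data from N=24 participants") and adds: "We will use this data to determine power requirements for a larger study".

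**The concern.** The tests named do not match the sampling described. Each participant contributes several methods, and some participants come from the same household, so there are two layers of dependence. Plain ANOVA has a place for neither.

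For a comparison of methods, the correlation that matters is the one in the difference (device minus criterion, or recall minus criterion), not in the raw values. It is most plausible in three places:

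- **Scale-based energy storage (ES) and Fitbit-derived energy intake (EI).** Drift or relocation of a shared scale affects everyone who stands on it.
- **Recalled EI.** Shared meals could lead to shared reporting error. This is an inference; the protocol does not say so.
- **Energy expenditure (EE).** The case is weaker here, because EE comes from a wrist-worn monitor.

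At stake is whether the P<.05 threshold means what it says. Repairing only the within-person layer, which is the obvious first correction, would leave the household layer unaddressed.

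**Working it through.** **Plan's own figure.** N=24 is a resource limit with no effect size, standard deviation or power behind it, so there is nothing to reproduce.

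**Inputs.** From the protocol: 24 people and two-sided alpha 0.05. Assumed, because the protocol gives neither: equal households of size m = 2, 3 or 4 (12, 8 or 6 households) and an ICC of the between-method difference of 0.1, 0.3 or 0.5.

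**Step 1: person-level paired comparison that ignores household.**

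- Design effect: DEFF = 1 + (m − 1) × ICC
- Effective n = 24 / DEFF
- Correct SE / naive SE = √DEFF
- Approximate true error = 2 × [1 − Φ(1.96 / √DEFF)]

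Middle case, m = 3 and ICC = 0.3: DEFF = 1 + 2 × 0.3 = 1.6; effective n = 24 / 1.6 = 15; SE ratio = √1.6 = 1.26; error = 2 × [1 − Φ(1.96 / 1.265)] = 12.1%.

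| m | ICC | DEFF | Effective n | SE ratio | Error, formula |
|---|---|---|---|---|---|
| 2 | 0.1 | 1.1 | 21.8 | 1.05 | 6.2% |
| 2 | 0.3 | 1.3 | 18.5 | 1.14 | 8.6% |
| 2 | 0.5 | 1.5 | 16.0 | 1.22 | 11.0% |
| 3 | 0.1 | 1.2 | 20.0 | 1.10 | 7.4% |
| 3 | 0.3 | 1.6 | 15.0 | 1.26 | 12.1% |
| 3 | 0.5 | 2.0 | 12.0 | 1.41 | 16.6% |
| 4 | 0.1 | 1.3 | 18.5 | 1.14 | 8.6% |
| 4 | 0.3 | 1.9 | 12.6 | 1.38 | 15.5% |
| 4 | 0.5 | 2.5 | 9.6 | 1.58 | 21.5% |

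Simulation of the paired test (40,000 runs per setting) agrees: about 6% at m = 2, ICC 0.1; about 12% at m = 3, ICC 0.3; and about 23% at m = 4, ICC 0.5. With ICC = 0 it gives about 5%. A test on household means gives about 5% in every setting.

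**Step 2: ANOVA taken literally, with method as an unpaired factor.** Let rho be the within-person correlation between two methods. The ratio of true to assumed variance of the method difference is (1 − rho) × DEFF. The test is conservative once rho exceeds 1 − 1/DEFF:

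- m = 2, ICC 0.1: 1 − 1/1.1 = 0.09
- m = 3, ICC 0.3: 1 − 1/1.6 = 0.375
- m = 4, ICC 0.5: 1 − 1/2.5 = 0.60

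Simulated error at m = 3, ICC 0.3:

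| rho | Error |
|---|---|
| 0 | 12.5% |
| 0.3 | 6.8% |
| 0.5 | 3.4% |
| 0.8 | 0.2% |

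**Step 3: can a shared scale matter when ES is a change score?** A constant offset cancels in the change; drift does not. By the intake equation in section 5, an assumed shared error of 0.1 kg in fat-mass change over 14 days gives 9,500 × 0.1 / 14 ≈ 68 kcal/day for everyone on that scale. If fat-free mass moves equally the other way, it is (9,500 − 1,020) × 0.1 / 14 ≈ 61 kcal/day.

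**Step 4: the variance handed to the larger study.** The naive person-level variance has expected ratio 1 − (m − 1) × ICC / 23 to the true one. At m = 3, ICC 0.3 this is 1 − 0.6 / 23 ≈ 0.97.

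**The case against.** Four stronger readings are tempting, and the protocol supports none of them.

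- **Every analysis treats the 24 people as independent.** No section says so. The dependence structure of the Bayesian calibration is not described, and a statistical analysis plan that is not at hand may include family effects. What the protocol does fix is the ANOVA and chi-square tests.
- **Standard errors and P values are certainly too small.** That requires a positive ICC in the method difference. Shared meals and activity largely move the true value that both methods see, so much of that sharing cancels. Under a literal unpaired ANOVA, high within-person correlation, which is plausible over ages 8 to 90, makes P values too large.
- **Validation leaks information between relatives.** No hold-out or cross-validation by person is planned. The reassessment in section 3 is a later 14-day period.
- **The pilot passes on a badly biased variance.** Step 4 shows a reduction of only about 3%. A design effect matters to the larger study only if that study also enrols families, which is not stated.

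It is also fair to say that recruitment is by flyer (section 6), so some households may contribute one person. The larger error rates in the table are assumptions that nothing in the protocol bounds, and this is a pilot with no powered hypothesis.

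These points limit the size and certainty of the problem but do not remove it. Family enrolment, the shared scale and the named tests are all stated, and the tests do not fit that sampling under either reading of ANOVA.

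**Conclusion.** The point holds in conditional form. The protocol specifies clustered sampling and several methods per person, then names tests that provide for neither.

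In a paired person-level analysis with equal households of 2 to 4 and ICC 0.1 to 0.5, the true error of a nominal 5% test is about 6% to 22%, and about 12% in the middle case. With ICC 0 there is no inflation. With fewer or smaller families it is less. In a literal unpaired ANOVA the error can fall on either side of 5%, depending on a within-person correlation that the protocol does not give.

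The concern is strongest for ES, Fitbit-derived EI and recalled EI, and weaker for EE. As this is a resource-limited pilot, it is something that should be corrected rather than a fatal flaw.

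**What to change.** - **Method comparisons.** In section 7, replace the plain ANOVA with a mixed model that has participant nested in household. Let the method difference vary by household, because a household intercept alone shifts all methods equally and drops out of the contrast. Household-clustered inference with a small-sample correction is an alternative. Any chi-square comparison needs the same allowance.
- **Calibration.** Carry the same household effect into the Bayesian model, if it is not already there, and say so.
- **Hold-out checks.** If any are done, keep whole households together.
- **Reporting.** Give the number and size of households, and the household ICC of the method differences with its interval. Use the ICC in sizing the larger study if that study also enrols families.

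**Cost.** The change needs a household identifier, and household membership has to be known anyway to issue the scales. Intervals will be wider than in a person-level paired analysis, by about 1.26 times at m = 3, ICC 0.3 and up to 1.58 times at m = 4, ICC 0.5. With perhaps 6 to 12 households, the ICC will be imprecise and should be presented that way.

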- Energy expenditure will be assessed using the doubly labelled water (DLW) technique over a two week period. The DLW technique uses enhanced levels of naturally occurring stable (i.e., non-radioactive) isotopes of hydrogen (deuterium; ^2H) and oxygen (^{18}O) to accurately measure energy expenditure via indirect calorimetry in free-living organisms. DLW was first introduced for human use in 1982. The method is safe and has been validated extensively in both humans and other animals (including children and infants). Participants will be administered a dose of DLW with 1.5 ml/kg body weight of a mixture of 10% enriched H_2^{18}O , and 99% enriched $^2\text{H}_2\text{O}$ (Cambridge Isotopes, Cambridge, MA). Participants will provide a urine sample (>15 mL) on day 0, 7, and 14, which will be analyzed by Pennington Biomedical Research Center to calculate elimination rates of the isotopes from the body.

Figure 1. Fitbit Alta HR (top) and Aria (bottom).

DXA Procedures

- Assessment of body composition, including fat mass, fat free mass, and visceral adipose tissue, will be completed using dual energy X-ray absorptiometry (DXA). DXA is a non-invasive procedure which participants will lie on a table and a detector will be passed over the body. The procedures involves approximately 1/3 the radiation in a normal chest X-ray and should take approximately 10 – 20 minutes. All anthropometric measurements will be performed with the participant dressed in surgical scrubs and in bare feet. BMI (weight [kg]/height [m]²) will be calculated from the average of three height and weight measurements using a wall-mounted stadiometer and electronic scale and recorded to the nearest 0.1 cm and 0.1 kg, respectively.

Diet Recalls

- Energy intake will be assessed subjectively via interviewer-administered dietary recalls. Three dietary recalls will occur on randomly selected non-consecutive days over each one-week treatment condition (including at least one weekend day) to minimize preparation that could bias recall by the participants. All interviews will be conducted over the telephone, will ask about all foods consumed over the previous 24 hours using a multi-pass approach, and energy intake will be calculated using the Nutrient Data System for Research software (NDSR Version 2014).

Records to be kept

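### Eligibility does not exclude pregnant or breastfeeding women: intake-balance EI is too low in breastfeeding, and pregnancy brings avoidable X-ray exposure

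*Protocol*

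**What the plan says.** Protocol Section 4 sets inclusion as "Healthy children and adults, aged 8-90", together with being able to be physically active. It adds: "We intend to enroll participants within the same family (child, parents, and siblings) as long as they meet the age criteria". The exclusions cover eating history, bariatric surgery, "or other significant medical diagnosis that could impact metabolism", and certain medications. Pregnancy and breastfeeding are not named there. Nor are they named in the visit descriptions in Section 6 or the phone screening in Section 8.

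Section 2 defines energy storage as intake minus expenditure. Section 5 turns this into one EI equation for every participant, with fixed coefficients: "1,020 represents the energy density in kcals of FFM per kg; and 9,500 represents the energy density of FM per kg".

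Section 5 schedules DXA on Day 0 and Day 14 of the two calibration periods and says of the scan: "The procedures involves approximately 1/3 the radiation in a normal chest X-ray". Section 6 places a DXA at visits 1 and 2 and then repeats the pattern: "Visit 3 will occur 4 weeks after visit 1. Procedures at visit 3 are identical to visit 1", with visit 4 matching visit 2.

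**The concern.** The exclusion list is evidently meant to keep out people whose metabolic state would upset the method. It lists diagnoses and drugs but omits two ordinary physiological states. Mothers of enrolled children are a group the study intends to recruit, and a healthy breastfeeding or pregnant mother meets every criterion on a plain reading.

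Two separate things are at stake:

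- **Breastfeeding.** Energy exported in milk is neither expended nor stored by the mother, so an equation built only on expenditure and storage cannot see it. This matters for absolute EI and for the claim in Hypothesis 2 that device-based EI is superior to self-report.
- **Pregnancy.** Gained fluid and tissue are valued as if they were the participant's own fat or fat-free mass at fixed densities. The participant would also have repeated X-ray scans that a simple eligibility question could avoid.

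**Working it through.** **Inputs from the Protocol.** N = 24 (Section 7). Identity ES = EI − EE (Section 2). EI = 1,020 × ΔFFM/Δt + 9,500 × ΔFM/Δt + EE, with Δt = 14 days per period (Section 5). DXA on two days in each of two periods (Section 5). Radiation per scan of about 1/3 of a chest X-ray (Section 5).

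**Assumptions, not in the Protocol.** Milk energy M = 300-500 kcal/d. EE = 2,200 kcal/d with stable body composition, used only for percentages. The reference EI for Hypothesis 2 is the intake-balance value from DLW and DXA. The Protocol states no figure of its own to reproduce on this point.

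**1. Breastfeeding: error in EI.** True balance is EI = ES + EE + M. The plan computes ES + EE. The error is therefore −M, or −300 to −500 kcal/d. Relative to true intake:
- −300 / (2,200 + 300) = −12.0%
- −500 / (2,200 + 500) = −18.5%

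**2. Effect on the mean of 24.**
- One participant: 300/24 = 12.5 and 500/24 = 20.8 kcal/d too low.
- Two participants: 600/24 = 25.0 and 1,000/24 = 41.7 kcal/d too low.

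**3. Which comparisons are affected.**
- Calibration: Section 5 calibrates Fitbit EE to DLW EE and Fitbit ES to DXA ES. M enters neither target, so there is no effect through this mechanism.
- Device EI minus reference EI: (Fitbit ES + Fitbit EE) − (DXA ES + DLW EE). M is missing from both sides, so the difference is unchanged.
- Self-report minus reference EI: an accurate recall equals ES + EE + M, so the difference is +M. A correct recall is scored as over-reporting by 300-500 kcal/d.

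**4. Pregnancy: error in EI.** Two illustrations, both on assumed values:
- Density error of 200-500 kcal/kg on an FFM gain of 0.4-1.2 kg per 14 days: from 200 × 0.4/14 = 5.7 to 500 × 1.2/14 = 42.9 kcal/d.
- Misassignment of 0.1-0.5 kg between FFM and FM: (9,500 − 1,020) × 0.1/14 = 60.6 to (9,500 − 1,020) × 0.5/14 = 302.9 kcal/d.

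The range runs from negligible to large, and the Protocol gives nothing that would narrow it.

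**5. Scans.** By period: 2 periods × 2 days = 4. By visit: one each at visits 1, 2, 3 and 4 = 4. The two counts agree. On the Protocol's own figure, 4 × 1/3 is about 1.3 chest X-rays.

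**The case against.** The strongest case on the other side is that this is a one-line clarification in a small, resource-limited pilot, and that the damage is easily overstated. Much of that stands.

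- A reader might infer that breastfeeding participants contaminate the calibration. They do not: the targets are EE and ES, and milk energy is in neither.
- A reader might infer that they become outliers in device error. They do not: the missing term cancels between device-based and DLW/DXA-based EI.
- A reader might infer that the equation fails by a known, large amount in pregnancy. The document supports a direction of concern but no size. Fluid booked as fat-free mass carries the low 1,020 kcal/kg value, which limits that route.
- A reader might infer that the study has no pregnancy check at all. Consent pages are not in the supplied text, and the phone-screen questions are not listed. The supportable statement is that no check appears in what was supplied.
- The shift in the mean is modest. By the plan's own equation, a 0.1 kg error in ΔFM over 14 days moves one person's EI by 9,500 × 0.1/14 = 68 kcal/d. Nothing in the Protocol says how many such women would enrol, and it may be none.
- The words healthy and significant medical diagnosis leave staff some discretion.

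The last argument does not close the gap. On a plain reading a healthy breastfeeding or pregnant woman has no such diagnosis. A radiation warning in a consent form would not deal with breastfeeding, and it would not replace an eligibility criterion, which belongs in the protocol rather than in an analysis plan.

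**Conclusion.** The point holds in limited form. Section 4 does not exclude pregnant or breastfeeding women although parents are a target group, and the supplied text shows no pregnancy check before any of four DXA scans.

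For breastfeeding, the understatement of EI follows from the Protocol's own identity and needs no outside evidence; only its size does. At an assumed 300-500 kcal/d, one participant of 24 lowers mean EI by about 13-21 kcal/d. The harm is confined to absolute EI and the self-report comparison in Hypothesis 2, given that the reference there is itself an intake-balance value. Because device and reference share the error, comparing the two cannot reveal it.

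For pregnancy, the EI error cannot be sized from the document. Avoidable X-ray exposure is the main reason to act, and that exposure is small on the Protocol's own figure.

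**What to change.** Add to the Section 4 exclusions: pregnant, planning pregnancy during the six-week study, or breastfeeding. Ask at the phone screen already described in Section 8 and reconfirm at visits where applicable. State that, if status changes, the affected periods are left out of the EI and ES analyses.

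The cost is one exclusion line, a short question and one sentence on data handling. The downsides are a slightly narrower pool of parents and a sensitive question for some participants. It needs particular care with minors, since enrolment starts at age 8 and the screening call is held with the parent.
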